1 OBJECTIVES

1.1 Purpose, Specific Aims, or Objectives

In this project, we will assess whether messaging about ventilation from cigarette filters lowers cigarette product appeal among smokers. This study, part of a series (I 50217, I 59617) will help determine whether a regulatory requirement to reduce ventilation will lower demand for cigarettes without unintended consequences. This project will assess the effect of variation in pack messaging about filter ventilation on consumers' rating of product appeal, perceptions of health risks, and changes in cigarette consumption in a 2-week field study. Our *premise* is that messaging about risks of filter ventilation will reduce the appeal of cigarette smoking and increase the likelihood that smokers would either quit smoking or switch to an alternative product (e.g., electronic cigarettes). This project is well-integrated with the other studies in this P01, using the same standardized research cigarettes with defined ventilation characteristics and design parameters, as well as relying on common biobehavioral measures.

The aim of the proposed study is to assess how adding messaging to cigarette packages about filter vents and filters influences respondents' awareness of filter ventilation, beliefs about the function of filter vents and filters, smoking behavior, ratings of cigarette satisfaction, smoking topography, exposure to nicotine and carbon monoxide, perceptions about the risk of smoking, and intention to stop smoking.⁶ The protocol will consist of a randomized experiment via two-week field study.

1.2 Hypothesis

We hypothesize that exposing smokers to messages about filter vents and filters will increase awareness and knowledge of the impact of filter ventilation on cigarette smoking behavior and increase intention to stop smoking. Exposure to messages on packs will also lower ratings of cigarette satisfaction but have no significant impact on smoking behavior, topography, and exposure to nicotine and carbon monoxide.

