11.2 Treatment

This study will use two types of cigarettes. One set of cigarettes are commercially available Marlboro cigarettes (Philip Morris USA, Richmond, VA), all combustible King size (83mm) cigarettes consisting of filler, filter paper, tipping paper, cigarette paper, tipping glue and seam glue. Specific varieties are listed in the table. Products will be sourced at retail from local outlets.

Alternatively, participants may receive investigational “roll your own” (RYO) cigarettes that will be prepared in the laboratory. These cigarettes will be made to match the commercially available Marlboro cigarettes. These cigarettes will be prepared with conventional tobacco (e.g., Good Stuff) rolled using an automatic rolling machine (e.g., Powermatic III+) and packaged into 20 rod packs. The investigational RYO cigarettes will use ventilated filter tubes (e.g., ~25-37% filter ventilation). The dose of nicotine in these RYO cigarettes will be similar to conventional cigarettes.

Within each pair of products is a nonmenthol and menthol equivalent. Participants who report regularly smoking menthol cigarettes will receive the menthol versions for the study.

Variety	Vent %	Filter length (mm)	Tobacco weight (mg)
Special Blend Smooth Mellow	30.6	27	625.1
Smooth Fresh Menthol	37.6	27	630.8

Additionally, cigarettes will be paired with messaging about filter ventilation. This message will be affixed to the front exterior of each package provided to participants.

- No Message (e.g., unaltered cigarette pack).
- Neutral Message: “Nothing about this product’s color or name means that it will protect a smoker from the health risks of smoking.”
- Compensation Message: “This product has a ventilated filter. Filter vents increase how deeply a smoker inhales without them knowing, which can increase the health risks of smoking.”
- Blocking Message: “This product has a ventilated filter. Be sure not to block the vent holes with your fingers or lips, which can increase the health risks of smoking.”

Roswell Park Protocol Number: I 757820

With these conditions, ‘no message’ serves as a true control (smoking as normal), while the neutral message serves as a control message to determine if added messaging impacts behavior/perceptions, even if that message is not informational. The compensation and blocking messages will determine if added messaging about the health risks of filter ventilation affect behavior/perceptions, and which type of message has the greater impact.

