11.3 Study Procedures

The proposed study is a between-subjects design in which participants will be randomized to 1 of 4 conditions for 2 weeks.

- No Message (e.g., unaltered cigarette pack).
- Neutral Message: “Nothing about this product’s color or name means that it will protect a smoker from the health risks of smoking.”
- Compensation Message: “This product has a ventilated filter. Filter vents increase how deeply a smoker inhales without them knowing, which can increase the health risks of smoking.”
- Blocking Message: “This product has a ventilated filter. Be sure not to block the vent holes with your fingers or lips, which can increase the health risks of smoking.

Data will be collected in three remote video sessions and via EMA conducted over 2 weeks. Each study session is expected to take 0.5 hours. For each condition, active data collection is expected to take no more than 15 minutes. Study materials (cigarettes, CO monitor, containers for cigarette filter collection, scales) will be mailed to, delivered, or picked up by participants. Session 1 will involve confirmation of receipt of study materials, questionnaires, and training on procedures. Then, participants will track their product use via EMA app (REDCap) for 2 weeks, with two remote sessions via videoconference for additional questionnaires.

Informed Consent. An initial videoconferencing session will be used for informed consent. Consent will be obtained through the REDCap (Research Electronic Data Capture) system used for data collection. REDCap is a secure web-based application that supports data capture and management for research studies. The Investigator and Research Associate will design the study specific consent and upload the most recent CRS versions to the REDCap system. A secure link will be sent to each participant prior to the start time of the study. Research staff will guide the participant form, provide time to read the consent, and answer any questions. Participants and staff will be able to electronically sign, data, and submit the consent in real-time. Once the consent is submitted, it is automatically saved on RPCI protected servers. Access to this folder is restricted to authorized users. Standard protocols for data encryption (via Credant) when using laptops and USB drives will be followed.

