22 STATISTICAL PLAN

22.1 Data Analysis Plan

The analysis of EMA data will be analyzed using a linear mixed model with fixed effects for vent message (product design, color/name), as well as sex and other tobacco product strata (cigarettes only or dual use). The effect of packaging will be tested using a Bonferroni-corrected type-I error rate of 0.008 (0.05/6) to account for all possible pairwise comparisons of packaging types. Data from the field-study (e.g., change in product responses, risk, TNE, aldehyde-DNA adducts) will be analyzed using linear regression with terms in the model for vent message (no message, neutral, compensation, blocking), sex, and other tobacco product use.. Categorical outcomes for the field-study will be analyzed using logistic regression. As exploratory approaches, we will use time-varying effects models (TVEMs) to explore the effect of message condition on smoking behavior (product compliance), craving, risk perception, and quit intention in the EMA data.[191, 192] TVEMs have been used previously to examine treatment effects on craving [193] and relapse.[194] TVEMs will provide daily effect sizes, thereby allowing us to examine whether treatment effects (and relationships with other predictors) change over time (i.e., early vs. later in product switching). Responses at Visit 1 can be treated as time invariant predictors and mCEQ from EMA can be treated as time-varying predictor (and/or outcome) of product use.

Roswell Park Protocol Number: I 757820

We will enroll a total sample size of 300 subjects and assume a 20% drop-out rate with uniform drop-out from Visit 1 to Visit 3. This will result in a sample size of 300 subjects for Visit 1, 270 subjects for the first week of the field study, and 240 subjects for the end of field study. Our sample size was determined to have adequate power for the field study, For the field study, we hypothesize a 25% difference between conditions, corresponding to a 3.9 CPD difference. Assuming a standard deviation of 7.6,[195] a sample size of 240 subjects will provide 95% power to detect a significant difference between ventilation conditions at the 0.05 level and 80% power to detect a significant difference between packaging conditions with a Bonferroni-corrected type-I error rate of 0.008.

mCEQ is scored using an established algorithm.⁹⁶ This results in 3 subscales (Psychological Reward, Relief, Reward) and 2 single items (Aversion, Respiratory sensation). Scores range from 1-7.

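### Section 22.1 pre-specifies no test of the two vent messages together against control, which is the question that sections 1.2 and 11.2 ask

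*Combined protocol and SAP*

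**What the plan says.** Section 1.2 treats vent and filter messages as one exposure: "We hypothesize that exposing smokers to messages about filter vents and filters will increase awareness and knowledge of the impact of filter ventilation". It adds higher intention to stop smoking and lower satisfaction ratings. For consumption and exposure it predicts that messages will "have no significant impact on smoking behavior, topography, and exposure to nicotine and carbon monoxide".

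Under section 11.3, "participants will be randomized to 1 of 4 conditions for 2 weeks". No allocation ratio is stated. Section 11.2 gives the arms their roles. No Message is the true control, and "the neutral message serves as a control message to determine if added messaging impacts behavior/perceptions". Of the other two arms it says: "The compensation and blocking messages will determine if added messaging about the health risks of filter ventilation affect behavior/perceptions". It also asks which of the two has the greater impact.

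In section 22.1, the EMA data get a linear mixed model, followed directly by a "Bonferroni-corrected type-I error rate of 0.008 (0.05/6) to account for all possible pairwise comparisons of packaging types". The other field-study data get linear regression with a four-level message term, or logistic regression for categorical outcomes. Those sentences name no contrast and no alpha. The power paragraph claims 95% power for "a significant difference between ventilation conditions at the 0.05 level" and 80% between packaging conditions at 0.008.

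The schedule in section 5.1 places vent awareness and the contemplation ladder at the video sessions only. Product evaluation, which carries satisfaction, is collected at the sessions and, for selected items, in EMA.

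**The concern.** The design asks three things: whether any added label matters, whether the vent messages matter, and which vent message is stronger. The second is the hypothesis of section 1.2, and it has no designated test. In the EMA analysis it is spread over four of the six pairs (each vent message against each control), with no rule for reading a pattern in which some pass and others do not. For awareness and quit intention no test is designated at all.

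The only statement that looks like power for a two-group comparison concerns ventilation conditions. Participants are randomized to messages. The two ventilation levels in the section 11.2 table belong to the nonmenthol and menthol varieties and follow the participant's own preference, so they are not randomized groups.

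At stake is whether the analyst chooses the test of the main hypothesis after seeing the data, and whether that test uses half of the sample (60 v 60) or all of it (120 v 120).

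**Working it through.** **Inputs.** From section 22.1: difference 3.9 CPD, SD 7.6, 240 completers, alpha 0.05/6 rounded to 0.008. Assumed, because not stated: equal allocation (240/4 = 60 per arm), two-sided tests, and a residual SD pooled over four arms (240 − 4 = 236 df). The standardized effect is 3.9/7.6 = 0.513 SD.

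**Formula.** Power = P(|T| > t_crit), where T is noncentral t with 236 df and noncentrality λ = δ/SE. Critical values are 2.675 at 0.008 and 2.714 at 0.05/7 = 0.00714.

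**Plan's own figures.**
- One pair, 60 v 60: SE = 7.6 × √(2/60) = 1.388, λ = 3.9/1.388 = 2.81. Power is 55.5% at 0.008, against the stated 80%.
- Two halves, 120 v 120, at 0.05: SE = 7.6 × √(2/120) = 0.981, λ = 3.97. Power is 97.7%, against the stated 95%.

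Neither figure reproduces. The 80% shortfall is a separate defect and adds no weight here.

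**Adding the pooled contrast.** Mean(Compensation, Blocking) − mean(No Message, Neutral) has the 120 v 120 SE of 0.981. All seven tests are at 0.05/7.

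| Test | λ | Power |
|---|---|---|
| Pooled contrast | 3.97 | 89.5% (90.1% by normal approximation) |
| One pair | 2.81 | 53.9% (from 55.5% at 0.008) |
| Vent messages v Neutral, 120 v 60; SE = 7.6 × √(1/120 + 1/60) = 1.202 | 3.25 | 70.2% |

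When no arm differs, at least one of the seven tests is significant in 3.8% of trials (400,000 simulated), so the family stays below 5%.

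**Where the pooled contrast misleads or fails.**
- Any label shifts the outcome by 3.9 and vent content adds nothing: the contrast is (3.9 + 3.9)/2 − (0 + 3.9)/2 = 1.95, λ = 1.95/0.981 = 1.99. It is significant in 23.6% of trials.
- Only one vent message works: the contrast is (3.9 + 0)/2 − 0 = 1.95, so power is again 23.6%. At least one of the four vent-v-control pairs is significant in 70% of trials at 0.05/7.

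**How the four vent-v-control pairs behave at 0.008.** Both vent arms differ equally from both controls; 400,000 simulated trials per row. Effects other than 0.513 SD are assumed.

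| Effect (SD) | None significant | One to three | All four |
|---|---|---|---|
| 0.2 | 83% | 17% | under 1% |
| 0.3 | 62% | 37% | 1% |
| 0.4 | 36% | 58% | 6% |
| 0.513 (plan) | 13% | 65.5% | 22% |
| 0.6 | 4% | 54% | 42% |
| 0.8 | under 1% | 14% | 86% |

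**The case against.** All-pairs testing is a legitimate and conservative choice with two distinct controls and two distinct messages. A four-level model can yield any contrast, so no information is lost by design. Both points stand: this is a gap in pre-specification, not a flaw in the design.

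A reader might infer that the whole hypothesis is tested only through six pairs at 0.008. The text does not say that. The rule follows the EMA model, and the session regressions state neither pairs nor an alpha, so for awareness and quit intention the test is undefined.

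A reader might also infer that the trial will usually give a mixed answer. That holds at the CPD planning effect and roughly from 0.4 to 0.6 SD. CPD is an outcome on which section 1.2 expects no effect, and the documents give no effect size for awareness, satisfaction or quit intention. At small effects usually no pair is significant, and at large effects usually all four are.

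The strongest objection is to pooling the controls. Section 11.2 includes Neutral to learn whether any label matters, and pooling presumes that it does not. The 23.6% figures for a general label effect and for a single effective message show the cost. This objection defeats the tempting step of replacing the six pairs with a few pooled contrasts. It does not defeat adding one contrast beside the pairs and limiting how it is read.

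**Conclusion.** The concern holds as a pre-specification gap. Sections 1.2 and 11.2 ask whether the vent messages as a class differ from control. Section 22.1 designates no test of that for any outcome, and it states a power for groups that the trial does not randomize.

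At the plan's CPD inputs, the missing contrast would have about 90% power at 0.05/7, against 55.5% for one pair at 0.008. Adding it lowers each pair by under 2 points. These sizes assume 60 completers per arm, two-sided tests and a shared effect of both messages, and they are illustrative for the outcomes that section 1.2 expects to change. The absence of the contrast does not depend on them.

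The material does not support dropping the pairs: if only one message works, they carry most of the power.

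**What to change.** In section 22.1, for both the EMA and the session models:

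1. Add one pre-specified contrast, the mean of Compensation and Blocking against the mean of No Message and Neutral, and name it as the test of section 1.2.
2. Keep the six pairs as confirmatory, and test all seven at 0.05/7 = 0.00714.
3. State that a positive pooled contrast is attributed to vent content only together with vent messages v Neutral (120 v 60) and Neutral v No Message. The 120 v 60 comparison is an extra condition on the interpretation, so it opens no new route to a positive claim.
4. Delete the power statement for ventilation conditions, and give the power of the pooled contrast with its allocation and sidedness.

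The cost is SAP wording and a few contrast statements in models already planned, with no new data or participants. Power per pair falls from 55.5% to about 54%. The pooled contrast stays weak if only one message works (about 24%), which is why the pairs remain confirmatory.

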2 BACKGROUND

2.1 Prior Experience and Gaps in Current Knowledge

The physical design features of cigarette products directly impact their appeal by influencing both cognitive and sensory perceptions. The introduction of a now common design feature, filter ventilation, has led to greater public harm than benefit because of the potential for greater toxicity while enhancing product appeal among smokers. Ventilated cigarettes dilute smoke, which promotes perceptions of "smoothness" and therefore lower health risk, contributing to the overall appeal of these products. Tobacco product appeal is driven by factors including abuse liability (i.e. the potential for tobacco products to initiate and maintain nicotine dependence), subjective responses (e.g., liking, satisfaction, taste perceptions), and perceptions of cigarette pack messaging and other marketing strategies (including normative beliefs, risk perceptions, perceived benefits, outcome expectancies, use intentions, & product purchase). These perceptions and beliefs are further shaped by cigarette manufacturers' use of descriptive terms and colors on packaging designs and advertising.

In this project, we will assess whether messaging about ventilation from cigarette filters lowers cigarette product appeal among smokers. This project is *significant* because it will generate

Roswell Park Protocol Number: I 757820

tobacco product regulatory science to support future policy approaches to filter ventilation that may reduce demand for cigarettes and the population harm associated with their use.

This project is *innovative* because it will generate novel science that informs our understanding on interactions between product physical design and messaging influence smokers' perceptions of the product appeal and health risk.

2.2 Relevant Preliminary Data

The PI ([name]) and the investigative team have extensive experience in examining biobehavioral responses to cigarette design. Pilot research relevant to the current proposal ([name], unpublished) assessed responses to "light" cigarettes and packaging. Participants (N=90) were current smokers whose brand of choice was Marlboro "Lights"/Gold. Using a factorial design, participants were randomized to receive a Marlboro "Lights" cigarette presented in one of three pack conditions 1) text descriptors present; 2) text descriptor removed; and 3) plain (brown) pack. Participants smoked two cigarettes, in counterbalanced order: 1) blocked and 2) unblocked. A significant interaction was observed between pack design and ventilation on measures of smoking *Effect* ($p=0.007$), with the ventilated cigarette producing greater perceived effect as pack descriptors were removed, and *Throat Impact* (a cue for nicotine delivery) ($p=0.039$). Pack design and ventilation also interacted to influence sensory perceptions of irritation, and taste ($p's < 0.017$), with higher ratings seen on plain packs with blocked ventilation.

[figure not shown]

Figure 1. Interaction of filter ventilation and pack descriptor on drug effect and liking measures.

Figure 1 shows that *variation in filter ventilation interacts with pack descriptors to influence drug effect and liking*. Web-based survey work (conducted in August-September 2016) funded under the prior COMET project (under protocol I 218912) included items on awareness of filter ventilation among smokers,¹¹³ and an administration of the mCEQ.⁹⁶ Among the 1986 current smokers in the sample, 44.7% were aware of filter vents in cigarettes, while 45.7% were unaware, and 9.7% replied 'don't know.' Smokers aged 18-34 were more likely than those aged 35+ to be aware of vents (49.9% vs. 32.4%, $<.001$). Men were substantially more likely than women to be aware of vents (60.1% vs. 30.0%, $p<.0001$). Most smokers (among those aware; $n=1079$) believed that covering the vents would make the cigarette taste stronger (58.6%), though 15% reported 'don't know.' Those aged 18-34 were slightly more likely to believe covering vents would make cigarettes stronger (59.9% vs. 52.1%), though older smokers were more likely to say 'don't know' (10.9% vs. 27.4%). All in all, these data suggest continued lack of awareness of filter ventilation among smokers. Overall, 30.4% of smokers believed their cigarette was lighter in taste than other

Roswell Park Protocol Number: I 757820

cigarettes on the market, and 29.7% believe their cigarettes were smoother on the throat. Nearly half (46.9%) reported that they enjoyed the taste of their cigarettes 'a lot.'

2.3 Scientific or Scholarly Background for, Rationale for, and Significance of the Research Based on the Existing Literature and How Will It Add to Existing Knowledge

An important design feature that separates cigarette brand variants is the degree of filter ventilation, achieved by the placement of holes in cigarette filters.¹⁻³ Filter ventilation has contributed to population harm by attracting new users and diverting existing smokers from quitting.^{4,11-16} Filter ventilation is deceptive in this regard because most smokers are unaware of it,¹⁸⁻²¹ and it promotes taking larger puffs by reducing resistance to draw.^{4,5,22} Smokers fingers and lips may also block vents during smoking, reducing or even eliminating the smoke dilution effect.^{4,23-29} Smokers of 'light' and 'ultralight' brands tend to take in similar levels of nicotine compared to 'regular' cigarette smokers, while often being exposed to higher concentrations of tobacco toxicants that reach deeper parts of the lung^{22,30-41} and likely contributing to a higher risk for lung adenocarcinomas. Unfortunately, many smokers continue to believe that 'low tar' cigarettes are less hazardous to their health.^{18,19,42-49} For all these reasons, scientists have called for restrictions on filter ventilation as a fundamentally harmful feature, which can be easily removed by cigarette manufacturers.

In order for the FDA to exert regulatory authority in this area, evidence is needed to demonstrate that regulations will benefit population health.⁵⁰ The effects of banning ventilated filters could have positive consequences. The unvented products may be rendered harsher to smoke and less appealing, which could decrease use and exposures and increase intentions to quit or substitution of less hazardous alternatives. On the other hand, removal could potentially lead to increased or similar levels of smoking behaviors and toxicant exposures among consumers because they adapt to the harsher smoke or because of higher reinforcing doses of nicotine.

[figure not shown]

Figure 2. Conceptual Framework

Product appeal and risk perception. Two inter-related domains drive consumer trial and adoption of tobacco products⁵⁴⁻⁶⁷, as illustrated in Figure 2. These include: i) *perceptions of product*

Roswell Park Protocol Number: I 757820

messaging, often communicated via the product packaging; and ii) *responses to product use*, which include both sensory and other subjective response measures. Taken together, these consumer responses reflect the combined effects of product design and branding, and the subsequent outcome of product use behavior.

Sensory factors in smoking. There is substantial evidence that sensory effects of smoking, such as harshness, smoothness, and taste of smoke, are important drivers of continued use. Initial work showed that sensory blockade reduced urge to smoke.^{87,88} Rose and colleagues examined various approaches to disassociate the nicotine and sensory components of smoking reward as approaches to cessation.⁸⁹⁻⁹⁵ Measurement approaches were developed to examine the upper airway sensory experience and factors associated with reward,^{92,93,95} which would later be refined into a modified Cigarette Evaluation Questionnaire.⁹⁶ The release of internal tobacco industry research revealed the extent to which sensory factors were studied as important components of cigarette design.^{55,68,97,98} Continued misperceptions of cigarettes with misleading descriptors (e.g., “light”, “ultralight”, “mild”) are likely due to the sensory characteristics such as strength and harshness/irritation^{4,9} and filter ventilation level is related to perceptions of the relative harshness and strength of cigarettes.^{40,41} Expectancies of positive sensory effects of smoking (e.g., look, feel, and taste) are predictive of smoking behavior and willingness to try different cigarettes.⁹⁹⁻¹⁰⁵ This suggests that misperceptions about safety may persist as long as there is a perceptible sensory difference between products. Despite the critical regulatory science need, there are few published methods for testing tobacco products,^{57,106-108} particularly as applied to a systematic evaluation of a potential product standard.

Summary & Scientific Premise. Cigarette product design directly impacts product appeal via cognitive and sensory perceptions. Ventilated cigarettes dilute smoke, which is perceived as “smoother” and thus having lower health risks, contributing to the overall appeal of these products. These perceptions and beliefs are shaped by descriptive terms and colors on used in cigarette packaging and advertising. The FDA, through the Family Smoking Prevention and Tobacco Control Act (FSPTCA),⁵⁰ has regulatory authority over tobacco products. This places cigarettes and other tobacco products under a public health regulatory framework.¹⁰⁹⁻¹¹¹ Section 907 of the Act relates to the agency’s ability to issue and enforce product standards. While there are substantial studies about the impact of filter ventilation on smokers’ perceptions, to date there are none about the impact of removing filter ventilation. Our *premise* is that messaging about filter ventilation will reduce the appeal of cigarette smoking and increase the likelihood that smokers would either quit smoking or move to alternative nicotine delivery systems (ANDS), e.g., e-cigarettes or nicotine replacement therapy.

